6.4.2 Economic analysis

Given the objective of the trial and limited available evidence in support of the NOTABLE strategy, only a within trial economic analysis will be carried out. The analysis will adopt an incremental approach in that data collection will concentrate on resource use and outcome differences between trial arms. As the majority of cost data are skewed, and the mean cost of each procedure is of importance, a bootstrapping approach will be undertaken in order to calculate confidence intervals

around the mean costs. As the time frame of the economic evaluation is not greater than one year, discounting is not required.

Uncertainty in the confidence to be placed on the results of the economic analysis will be explored by estimating cost-effectiveness acceptability curves. These plot the probability that the intervention is cost-effective against threshold values for cost-effectiveness. The robustness of the results will be explored using sensitivity analysis. This will explore uncertainties in the trial based data itself, the methods employed to analyse the data and the generalizability of the results to other settings.

We will seek the assistance of an expert in health economics at the University of Ghent, Belgium.

6.5. Definition of the end of trial

The end of the NOTABLE trial will be defined as the time when the last participant recruited has completed 6 months of follow up.

7. ASSESSMENT OF PATIENT ACCEPTABILITY

7.1. Measurements for Patient Acceptability

The acceptability of vNOTES will principally be assessed using a questionnaire designed specifically for the study and administered within 24 hours of treatment to limit recall bias. Pilot testing will be carried out to make certain the questionnaire is usable. In addition to the questionnaire, data will be collected on the women who do not give consent to randomization (state a preference and agree to be registered for the NOTABLE study), and requested from those who decline to participate.

In order to aid interpretation and understanding of the questionnaire data, and to gain greater depth of experience, the acceptability of NOTABLE will further be assessed using a qualitative methodology. Interviewing after discharge will allow the woman time to reflect on her experience, and will also minimise the chance that gratitude to doctors and other hospital staff results in unduly positive responses. Honesty is also more likely to occur on neutral or the patient's home ground. Interviews will be recorded with patients' permission and transcribed verbatim. The interview schedule will be designed following a literature search on patient acceptability of surgical procedures, and from the focus group discussions. From these, a set of items will be derived which will seem relevant to the participants and cover all the areas thought to be important by participants. The latter will also ensure that the questionnaire is as discriminatory as possible. The interview schedule will be piloted with five women. These procedures will ensure face and content validity, and sending each woman the transcript of her interview with the opportunity to amend any inaccuracy will assess fair and accurate representation.

7.1.1 Sampling of Participants for In-depth Interview

We propose to select a 20% random sample (6 women) from each arm of the research for interview within one week of discharge either face to face, or by telephone.

7.2. Evaluation of Patient Acceptability

Analysis of data will be by content analysis with the development of analytical themes. The initial process will be the intensive reading and re-reading of interview transcripts, and a search for regularities, contradictions, patterns and themes by comparing the participants' statements using a coding frame. Inter-rater reliability on the coding of transcripts will be undertaken. A percentage of the transcripts will be coded independently by two members of the qualitative research team and discrepancies discussed and resolved. Emergent themes obtained by this process will be refined until final themes are agreed by all applicants as reflective of the data. 'Researcher triangulation' will offer the first step to verification of the findings. This will be achieved through the independent analysis of 20% of transcripts from the sample by the researchers. Verification occurs through discussion of their analyses, comparison and subsequent consensus. 'Respondent validation' will also be sought by

taking the tentative findings back to a sample of participants in order to be verified as reflective of their experience. A final form of verification is the comparison of findings with, and their embeddedness in the available literature.

It is anticipated that the questionnaire and the subsequent in depth interviews will measure and provide insight into acceptability and satisfaction in the following areas: the procedure(s) for diagnosis; the information provided when consent is obtained; procedures to protect confidentiality; preference for one arm of the trial over the other; experience of the procedure and the immediate post-operative phase; overall satisfaction with the process; acceptability for the same procedure if adnexal masses are diagnosed in the future; perceptions of being involved in an RCT.

8. DATA ACCESS AND QUALITY ASSURANCE

8.1. In-house Data Quality Assurance

The study will adopt a centralized approach to monitoring data quality and compliance. A computer database will be constructed specifically for the study data and will include range and logic checks to prevent erroneous data entry. Independent checking of data entry of paper questionnaires will be periodically undertaken on small sub-samples. The trial statistician will regularly check the balance of allocations by the stratification variables. Source data verification will only be employed if there is reason to believe data quality has been compromised.

8.2. Independent Trial Steering Committee

The Trial Steering Committee (TSC) provides independent supervision for the trial, providing advice to the Chief and Co- Investigators on all aspects of the trial and affording protection for patients by ensuring the trial is conducted according to the MRC Guidelines for Good Clinical Practice in Clinical Trials.

If the Chief and Co-Investigators are unable to resolve any concern satisfactorily, Principal Investigators, and all others associated with the study, may write through the Trial Office to the chairman of the TSC, drawing attention to any concerns they may have about the possibility of particular side-effects, or of particular categories of patient requiring special study, or about any other matters thought relevant.

8.3. Data Monitoring and Ethics Committee: Determining when clear answers have emerged

If vNOTES is clearly inferior to standard laparoscopic treatment, with respect to the primary endpoint, then this may become apparent before the target recruitment has been reached. Alternatively, new evidence might emerge from other sources that vNOTES definitely more, or less, effective than laparoscopy. To protect against this, during the period of recruitment to the study, interim analyses of major endpoints will be supplied, in strict confidence, to an independent Data Monitoring and Ethics Committee (DMEC) along with updates on results of other related studies, and any other analyses that the DMEC may request. The DMEC will advise the chair of the Trial Steering Committee if, in their view, any of the randomised comparisons in the trial have provided both (a) “proof beyond reasonable doubt” that for all, or some, women that vNOTES is so inferior from laparoscopy that non-inferiority can never be demonstrated, and (b) evidence that might reasonably be expected to influence the patient management of many clinicians who are already aware of the other main trial results (b) evidence that might reasonably be expected to influence the patient management of many clinicians who are already aware of the other main trial results. The TSC can then decide whether to close or modify any part of the trial. Unless this happens, however, the Trial

management group (TMG), TSC, the investigators and all of the central administrative staff (except the statisticians who supply the confidential analyses) will remain unaware of the interim results.

9. ORGANIZATION AND RESPONSIBILITIES

All investigators are responsible for ensuring that any research they undertake follows the agreed protocol, for helping care professionals to ensure that participants receive appropriate care while involved in research, for protecting the integrity and confidentiality of clinical and other records and data generated by the research, and for reporting any failures in these respects, surgical complications and other events or suspected misconduct through the appropriate systems.

9.1. Centre eligibility

Not applicable since NOTABLE is a single centre RCT.

9.2. Local Coordinator

The responsibilities of the local Principal Investigator will be to ensure that all medical and nursing staff involved in the care of NOTABLE are well informed about the study and trained in trial procedures, including obtaining informed consent. The local Principal Investigator should liaise with the Trial Coordinator on logistic and administrative matters connected with the trial.

9.3. Nursing Coordinator

One nurse will be designated as *local Nursing Coordinator*. This person would be responsible for ensuring that all eligible patients are considered for the trial, that patients are provided with patient information sheets, and have an opportunity to discuss the study if required. The nurse may be responsible for collecting the baseline patient data and will act as a contact for obtaining missing follow-up evaluations. Again, this person would be sent updates and newsletters, and would be invited to training and progress meetings.

9.4. The NOTABLE Trial Office

The Trial Office at department of Obstetrics and Gynaecology of the participating centre is responsible for providing all trial materials, including the trial folders containing centre specific trial documentation, standard operating procedures and training materials. Additional supplies of any printed material can be obtained on request or downloaded from the NOTABLE trial website. The Trial Office is responsible for collection and checking of data (including reports of serious surgical complications), for reporting of serious adverse events to the sponsor and/ or regulatory authorities and for analyses. The Trial Office will help resolve any local problems that may be encountered in trial participation.

9.5. Research Governance

The study will be conducted according to the principles of the Declaration of Helsinki (Adopted by the 18th WMA General Assembly, Helsinki, Finland, June 1964, and amended by the 52nd WMA General Assembly, Edinburgh, Scotland, October 2000) and in accordance with the Belgian law of 7 May 2004 that regulates human experiments in Belgium.

All Principal Investigators will be required to sign an Investigator's Agreement, detailing their commitment to accrual, compliance, Good Clinical Practice, confidentiality and publication. Deviations from the agreement will be monitored and the TSC will decide whether any action needs to be taken, e.g. withdrawal of funding, suspension of centre.

9.6. Research Governance and Ethical Approval

As the trial does not involve an investigational medicinal product, clinical trial authorization from the Medicines and Healthcare products Regulatory Authority is not required.

In accordance to the Belgian law of 7 May 2004 that regulates human experiments, the investigator will inform the study participants and the medical ethical committee if anything occurs, on the basis of which it appears that the disadvantages of participation may be significantly greater than was foreseen in the research proposal. The study will be suspended pending further review, except insofar as suspension would jeopardize the subjects' health. The investigator will take care that all subjects are kept informed.

The principal investigator will report all adverse and serious events to the medical ethical committee.

Adverse events are defined as any undesirable experience occurring to a participant during the study, whether or not considered to be related to the intervention.

All adverse events reported spontaneously by the participant or observed by the investigator or his staff will be recorded.

A serious adverse event is any untoward medical occurrence or effect that:

- results in death;
- is life threatening (at the time of the event);
- requires hospitalization or prolongation of existing inpatients' hospitalization;
- results in persistent or significant disability or incapacity;
- is a congenital anomaly or birth defect;
- is a new event of the trial likely to affect the safety of the subjects, such as an unexpected outcome of an adverse reaction, lack of efficacy of an IMP used for the treatment of a life threatening disease, major safety finding from a newly completed animal study, etc.

All SAEs will be reported to medical ethical committee that approved the protocol, within 15 days after the investigator has first knowledge of the serious adverse reactions.

SAEs that result in death or are life threatening should be reported expedited. The expedited reporting will occur no later than 7 days after the responsible investigator has first knowledge of the adverse reaction. This is for a preliminary report with another 8 days for completion of the report.

All adverse events will be followed until they have abated, or until a stable situation has been reached. Depending on the event, follow up may require additional tests or medical procedures as indicated, and/or referral to the general physician or a medical specialist.

9.7. Funding and Cost implications

The research costs of this non-commercial trial are funded by the investigating team.

9.8. Indemnity

No additional preoperative examinations are needed when compared to the situation where the woman would not have given informed consent for study participation. One additional postoperative examination is needed for study participants compared to routine clinical practice: no risks or side effects are associated with this additional assessment. The risks and side effects for both types of surgical interventions have been extensively described in the consent form. According to two large prospective studies the incidence of complications associated with minimally invasive surgery are less than 1%. (26, 27) The benefit is an, as of yet, unknown increase in the chance of being discharged the same day as the surgical procedure with less postoperative pain.

The investigators have a 'no fault' liability insurance which is in accordance to the Belgian law of 7 May 2004 that regulates human experiments. The insurance aims to cover the financial consequences of the civil liability that the investigators may incur even when no fault has occurred as a result of the organization of medical experiments on the human person. All physical and material damage sustained by the participant in the experiment and/or his/her assignees and arising from the insured experiment are covered for an amount of 2 500 000 € per experiment. The insurance applies to the damage that becomes apparent during the study or within 36 months after the end of the study.

9.9. Publication

A meeting will be held after the end of the study to allow discussion of the main results among the collaborators prior to publication. The success of the study depends entirely on the wholehearted collaboration of a dedicated team of doctors, nurses and others.

9.10. Ancillary studies

It is requested that any proposals for formal additional studies of the effects of the trial treatments on some participants (e.g. special investigations in selected hospitals) be referred to the Trial

Management Committee for consideration. In general, it would be preferable for the trial to be kept as simple as possible, and add-on studies will need to be fully justified.

APPENDIX I: TABLE I

Table 1 Overview of patient and perioperative characteristics

Data	Mean	Range
Age (years)	51	31 - 75
BMI (kg/m ²)	24.0	17.2 - 28.7
Total operating time (min)	32	20 - 50
Serum hemoglobine drop (g/dl)	0.9	0 - 2.1
Postoperative pain score 6h	2.0	0 - 4
24h	1.3	0 - 2
Size of adnexal mass (mm)	51.8	35 - 110

APPENDIX III

CLAVIEN-DINDO CLASSIFICATION

[figure not shown]
TABLE 1. Classification of Surgical Complications

Grade	Definition
Grade I	Any deviation from the normal postoperative course without the need for pharmacological treatment or surgical, endoscopic, and radiological interventions Allowed therapeutic regimens are: drugs as antiemetics, antipyretics, analgetics, diuretics, electrolytes, and physiotherapy. This grade also includes wound infections opened at the bedside
Grade II	Requiring pharmacological treatment with drugs other than such allowed for grade I complications Blood transfusions and total parenteral nutrition are also included
Grade III	Requiring surgical, endoscopic or radiological intervention
Grade IIIa	Intervention not under general anesthesia
Grade IIIb	Intervention under general anesthesia
Grade IV	Life-threatening complication (including CNS complications)* requiring IC/ICU management
Grade IVa	Single organ dysfunction (including dialysis)
Grade IVb	Multiorgan dysfunction
Grade V	Death of a patient
Suffix "d"	If the patient suffers from a complication at the time of discharge (see examples in Table 2), the suffix "d" (for "disability") is added to the respective grade of complication. This label indicates the need for a follow-up to fully evaluate the complication.

*Brain hemorrhage, ischemic stroke, subarachnoidal bleeding, but excluding transient ischemic attacks.
CNS, central nervous system; IC, intermediate care; ICU, intensive care unit.

APPENDIX IV

CONSORT 2010 Flow Diagram

APPENDIX V Pain protocol**PROTOCOL ADNEXECTOMY – [name]
ASA I & ASA II PATIENTS**

1. INDUCTION ANEASTHESIA

- Propolipid 2,5mg/kg
- Sufentanil 0,15µg/kg
- Rocurorium 0,6mg/kg
- Dexamethasone 5mg
-

[figure not shown]
2. MAINTENANCE ANESTHESIA

- O₂/ room air 50/50
DES 1 MAC
- Need be Alfentanil 5mg/kg one shot
- 30min. before end surgery IV shot
 - 1g Paracetamol
 - Ketorolac 0,5mg/kg (maximum dose 30mg)

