3.2. Determining eligibility

All women regardless of age and parity presenting with a symptomatic or asymptomatic persistent benign adnexal mass on clinical examination who provide consent to participation are eligible in the NOTABLE trial based on the findings of the ultrasound findings and will be randomised before the procedure.

The following inclusion/exclusion criteria will be applied to assess eligibility:

Inclusion criteria:

- All women regardless of age and parity with a symptomatic adnexal mass presumed to be benign based on ultrasound examination by applying the IOTA simple rules
- All women regardless of age and parity with an asymptomatic persistent adnexal mass presumed to be benign based on ultrasound examination by applying the IOTA simple rules

- Written informed consent obtained prior to surgery

Exclusion criteria:

- History of hysterectomy by any technique
- History of rectal surgery
- Suspected rectovaginal endometriosis
- Suspected endometriotic cyst
- Solid adnexal mass
- High suspicion of adnexal malignancy based on clinical, ultrasound or biochemical findings
- History of pelvic inflammatory disease, especially prior tubo-ovarian or pouch of Douglas abscess
- Active lower genital tract infection e.g. Chlamydia, N. gonorrhoeae
- Virginity
- Pregnancy
- Need for other uterine surgical intervention (i.e. endometrial ablation, resection, myomectomy or hysterectomy)
- Additional pathology necessitating hysterectomy
- Failure to provide written informed consent prior to surgery

Obesity (Body Mass Index or BMI > 30), nulliparity or large diameter of the cyst are not considered to be an exclusion criterion per se. We will only stratify for the diameter of the cyst because this parameter was perceived by the gynaecological surgeon as the most important one to influence the difficulty of the procedure. Stratification for three parameters in a small pilot randomised trial with a limited number of participants is not sensible.

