using a reusable bipolar grasping forceps before being cut using cold scissors. The ovarian ligament is coagulated and cut. The infundibulopelvic ligament is coagulated and cut. The adnexa is resected. If necessary, the same procedure is repeated for the contralateral side. The peritoneal cavity is rinsed and haemostasis is checked.

Small and benign adnexa will be removed directly through the wound protector part of the NOTES port. Large adnexa or adnexa that are macroscopically suspicious, will be placed in an endobag (Memobag, Teleflex). The purse string of the endobag is pulled through the wound protector and the purse string is released. The content of the cyst is aspirated to reduce the volume of the adnexa. The endobag is now removed with the adnexa inside it. The vNOTES port is removed.

The colpotomy is closed using three interrupted figure-of-eight Vicryl 2/0 sutures. A vaginal plug (betadine gauze 10cmx5m) is placed to be removed after 3 hours together with the Foley catheter.

Antibiotic administration:

Cefazolin 2g and metronidazol 1.5g are administered IV during the procedure.

Analgesia at the recovery room and the nursing ward: The pain management for both groups was discussed with two senior staff members of the department of anaesthesiology of the hospital, who are co-investigators. The protocol will be standard for both comparison groups and is presented in appendix V.

The vaginal plug and the Foley catheter are removed 3 hours after the surgery. The bandages are left in place and not changed unless soaked by blood with a need to change. The personnel of the recovery room will be asked to replace bandages only for hygienic reasons and immediately to apply a new wound dressing without revealing any information to the participant or personnel on the outpatient or hospitalization ward.

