3. POSTOPERATIVE PHASE**RECOVERY**

- If VAS >4: 1g Paracetamol IV
- Reevaluation after 30min.
 - If VAS >4: 2,5mg Piritramide IV

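### Appendix V prints the as-needed intra-operative alfentanil supplement as 5 mg/kg in one shot, a likely mg-for-µg unit error to be checked against the source page

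*Protocol*

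**What the plan says.** Appendix V is headed as the adnexectomy protocol for ASA I and II patients. It runs through induction, maintenance and recovery as one regimen and does not distinguish the arms.

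- Induction lists "Propolipid 2,5mg/kg" and "Sufentanil 0,15µg/kg", then rocuronium at 0.6 mg/kg and a flat 5 mg of dexamethasone.
- Maintenance has the line in question: "Need be Alfentanil 5mg/kg one shot". It also lists flat-dose paracetamol and ketorolac at 0.5 mg/kg, limited to 30 mg.
- Recovery has a flat-dose rescue step: "If VAS >4: 2,5mg Piritramide IV".

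Sections 4.1.1 and 4.1.2, one for each arm, carry the same sentence: "The protocol will be standard for both comparison groups and is presented in appendix V". In both places it follows a lead-in about analgesia in the recovery room and on the ward. No other section of the protocol restates, limits or corrects an alfentanil dose.

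**The concern.** This is a dosing line in the regimen that staff are meant to use, not background text. Read against its neighbours, it looks out of scale. An optional opioid top-up is printed at a higher per-kg dose than the drug used to induce anaesthesia, and in a unit a thousand times larger than the one used for the other intra-operative opioid.

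If the source page does read mg/kg and someone follows it literally, any woman given the supplement is exposed to a serious dosing hazard. What is at stake is participant safety, not the inference about the primary outcome.

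**Working it through.** The protocol derives no absolute alfentanil dose, so there is no figure of its own to reproduce. The check is arithmetic on the printed doses.

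**Inputs**

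- Alfentanil: 5 mg/kg, one shot, as needed (Appendix V, maintenance).
- Sufentanil: 0.15 µg/kg; Propolipid: 2.5 mg/kg (Appendix V, induction).
- Body weight: 50 to 90 kg. This is an assumption. Section 3.2 states "Obesity (Body Mass Index or BMI > 30), nulliparity or large diameter of the cyst are not considered to be an exclusion criterion per se", so heavier women can be enrolled.

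**Dose as printed** (dose per kg × weight)

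- 50 kg: 5 × 50 = 250 mg
- 70 kg: 5 × 70 = 350 mg
- 90 kg: 5 × 90 = 450 mg

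**Same number read in micrograms** (illustration only)

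- 50 kg: 5 × 50 = 250 µg = 0.25 mg
- 70 kg: 5 × 70 = 350 µg = 0.35 mg
- 90 kg: 5 × 90 = 450 µg = 0.45 mg

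The two readings differ by a factor of 1000.

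**Comparison inside the appendix**

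- Against the induction agent: 5 / 2.5 = 2, so the as-needed supplement is printed at twice the Propolipid dose per kg.
- Against sufentanil as printed: 5 mg/kg = 5000 µg/kg, and 5000 / 0.15 is about 33,000.
- Against sufentanil if the unit were µg/kg: 5 / 0.15 is about 33.
- Sufentanil in absolute terms: 0.15 × 50 = 7.5 µg to 0.15 × 90 = 13.5 µg.

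These ratios show the scale of the mismatch. They do not give the right dose, because the protocol contains no potency or reference dose for alfentanil.

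**Units used for the weight-based drugs in Appendix V**

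| Drug | Printed dose | Maximum stated |
|---|---|---|
| Propolipid | 2.5 mg/kg | no |
| Sufentanil | 0.15 µg/kg | no |
| Rocuronium | 0.6 mg/kg | no |
| Alfentanil | 5 mg/kg | no |
| Ketorolac | 0.5 mg/kg | 30 mg |

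Four of the five are printed in mg/kg, and alfentanil has the largest per-kg figure of all five. Only one of the five has a maximum.

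**The case against.** The strongest reply is that the documents do not prove an error. They give no reference dose for alfentanil. A different unit for a different drug shows nothing by itself, and mg/kg is the usual unit in this appendix, shared by Propolipid, rocuronium and ketorolac. Grouping alfentanil with sufentanil as opioids is general drug-class knowledge, and the comparison with the induction agent crosses drug classes. The text also comes from a PDF, so a µ may have been misread. All of this stands, and it is why the point is put as likely and begins with a check of the source page. Against it, the µ in the sufentanil line came through intact, and an optional top-up at twice the per-kg induction dose is hard to explain as intended.

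A reader might take three further steps that the protocol does not support.

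- **The missing maximum shows a slip.** It does not. Ketorolac is the only weight-based drug of the five with a cap, so having none is the norm in this appendix.
- **The protocol expressly orders this dose in both arms.** The sentence in Sections 4.1.1 and 4.1.2 concerns analgesia after surgery. That the intra-operative line covers both arms is a fair inference from how Appendix V is headed and laid out, but it is not stated.
- **The intended dose is 5 µg/kg.** The unit is probably µg/kg, but the number cannot be derived from the documents.

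It can also be said that an anaesthetist would notice, the more so as two senior anaesthesiology staff took part in setting the pain management. That lowers the chance of harm. It does not make the written line right.

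**Conclusion.** The point holds as a likely unit error in a dosing instruction. As printed, the supplement amounts to 250 to 450 mg in one shot at an assumed 50 to 90 kg, and more above that range. If mg stands where µg was meant, the line is wrong by a factor of 1000.

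The printed text and the arithmetic are certain, provided the PDF was read correctly. The unit error is an inference from two comparisons within Appendix V, so confidence is moderate. It should be fixed because the potential harm is serious and the check is cheap.

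A reader might also infer that trial results are at risk. They are not: the appendix sets one regimen without separating the arms, and the primary outcome, sample size, analysis and between-arm comparison do not depend on this line.

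**What to change.** The anaesthesiology co-investigators check the alfentanil line on the source page of Appendix V.

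- If it reads mg/kg, they correct dose and unit by a one-line amendment. The unit is most likely µg/kg, and the dose is for them to confirm. Staff who hold the current version are notified.
- If it already reads µg/kg, nothing changes.

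No maximum dose needs to be added. The cost is one check and, if needed, one amended line with a notice to staff.
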